5.1.2 Risks Associated with Emicizumab

5.1.2.1 Identified Risks

Thrombotic Microangiopathy (Associated with Emicizumab and aPCC)

Thrombotic microangiopathy is a very rare, but serious condition whereby microvascular thrombosis leads to organ damage.

As of October 2018, among 417 patients in five studies (ACE002JP, BH29884, BH29992, BH30071, and BO39182), there were 3 patients (1.0%), all in Study BH29884, who experienced thrombotic microangiopathy while receiving emicizumab prophylaxis. These events are believed to be caused by an interaction between emicizumab and aPCC, as all 3 patients received cumulative doses of >100 U/kg/day on average of aPCC for ≥24 hours for the treatment of breakthrough bleeds just prior to developing symptoms. These events were reported as serious adverse events (two Grade 4 events and one Grade 3 event). One patient died due to a serious adverse event of Grade 4 rectal haemorrhage (assessed as unrelated to emicizumab). From additional analyses, including data on the thrombotic microangiopathy and thromboembolic events,

there is evidence to support a drug-drug interaction between aPCC and emicizumab. Please see the Emicizumab Investigator's Brochure for a complete summary of safety information.

Specific guidance regarding the use of bypassing agents in combination with emicizumab is detailed in Section 4.4.1.

Any thrombotic microangiopathy event should be reported as an adverse event of special interest and also as a serious adverse event, if it meets criteria for such (see Section 5.2.2 and Section 5.2.3).

Guidelines for management of patients who develop thrombotic microangiopathy are provided in Section 5.1.3.

Hypercoagulation and Risk of Thrombosis

As of October 2018, four thromboembolic events have been reported in 3 patients with hemophilia A with inhibitors while receiving emicizumab in Study BH29884.

Two patients who administered cumulative doses of > 100 U/kg/day on average of aPCC for ≥24 hours while receiving emicizumab developed thromboembolic events. The thromboembolic events were reported as serious adverse events (Grade 3 cavernous sinus thrombosis, Grade 3 skin necrosis, and Grade 2 thrombophlebitis superficial); however, none were life-threatening or fatal. No anticoagulation was started and symptoms in both patients improved with supportive care. These adverse events are believed to be caused by a drug-drug interaction between emicizumab and aPCC.

5.1.2.2 Potential Risks

Life-Threatening Bleeding Due to Unreliable Standard Coagulation Tests and Inhibitor Assays in the Setting of Emicizumab

Coagulation laboratory tests (including, but not limited to, aPTT, one-stage FVIII activity, and FVIII inhibitor measurement on the Bethesda assay) are not reliable and do not accurately reflect a patient's underlying hemostatic status while receiving emicizumab prophylaxis. Owing to the long half-life of emicizumab, these effects on coagulation assays may persist for up to 6 months after the last dose.

There is a risk of life-threatening bleeding due to unreliable standard coagulation tests and inhibitor assays in the setting of emicizumab if a patient is treated by practitioners

other than emicizumab-prescribing practitioners in settings such as an emergency room or in an acute care setting.

Emicizumab mechanism of action and resulting interference were clearly demonstrated in a wide variety of coagulation laboratory tests approved for in vitro diagnostic use. Clinical trials also demonstrated the effects of emicizumab on laboratory tests. However, as of October 2018, no instances of under-treatment of bleeding events due to unreliable standard coagulation tests and inhibitor assays in the setting of emicizumab had been observed.

See Section [5.1.4](#) for interpretation of coagulation assays for patients receiving emicizumab.

Anaphylaxis, Anaphylactoid, and Systemic Hypersensitivity Reactions

Since emicizumab is a biological product, acute, systemic hypersensitivity reactions, including anaphylaxis and anaphylactic reactions, may occur. In completed and ongoing clinical studies of emicizumab, no severe hypersensitivity reactions have been reported. These events should be reported as Serious Adverse Events or Adverse Events of Special Interest as described in Section [5.2.3](#).

Patients with a history of hypersensitivity associated with monoclonal antibody therapies or to the components of the emicizumab injection will be excluded from study participation. HCPs administering the study medication in the clinic must be trained in the appropriate administration procedures, be able to recognize the signs and symptoms associated with potential hypersensitivity, anaphylactic, and anaphylactoid reactions, and should be familiar with Sampson's criteria for defining anaphylaxis (Sampson et al. 2006; see [Appendix 7](#)).

HCPs should also instruct patients how to recognize the signs and symptoms of hypersensitivity, anaphylactic, and anaphylactoid reactions and to contact an HCP or seek emergency care in case of any such occurrence. Patients/caregivers will also receive two alert cards to remind them of this information and these instructions should any of these reactions occur.

For patients with a previous history of a clinically significant hypersensitivity reaction, after each of the first three doses, the site will call the patient 24 hours after each dose to assess the status of the patient. Additional precautions following each of these doses may also be considered including having an extended observation period or IV access prior to dosing, etc. The investigator may include these or other precautions, as deemed appropriate.

Guidelines for management of patients who develop anaphylaxis, anaphylactoid, and systemic hypersensitivity reactions are provided in Section [5.1.3](#).

Immunogenicity

As with administration of any exogenous protein, a potential exists for the development of ADAs. Such antibodies can be neutralizing and/or sensitizing, producing the potential for reduced efficacy and/or allergic reactions. As discussed in Section 1.2.2.4, patients with hemophilia were reported to have positive ADAs. There were 4 positive ADA patients with declining PK profiles (ADA with neutralizing potential) of which one discontinued due to lack of efficacy. For additional information please see the Emicizumab Investigator's Brochure.

5.1.3 Management of Patients Who Experience Specific Adverse Events

Guidelines for management of specific adverse events are outlined in [Table 4](#).

Table 4 Guidelines for Management of Patients Who Experience Specific Adverse Events

Event	Action to Be Taken
Thrombotic Microangiopathy	
• Please see Section 3.1 and Section 3.3.3 for guidance on management of breakthrough bleeds, including required laboratory monitoring.• HCPs should be vigilant for patients who exhibit signs/symptoms consistent with thrombotic microangiopathy and immediately begin work-up and treatment, as per local guidelines.• If a patient has a thrombotic microangiopathy event, further administration of study drug should be interrupted. The decision to resume emicizumab after an event of thrombotic microangiopathy must be discussed with the Medical Monitor.
Hypercoagulation and Thromboembolic Events	
• Please see Section 3.1 and Section 3.3.3 for guidance on management of breakthrough bleeds, including required laboratory monitoring.• HCPs should be vigilant for patients who exhibit signs/symptoms consistent with thromboembolic events and immediately begin work-up and treatment, as per local guidelines.• If a patient has a thromboembolic event, administration of study drug should be interrupted. The decision to resume emicizumab after a thromboembolic event must be discussed with the Medical Monitor.
Injection-Site Reaction	
• Injection-site reactions should be treated as clinically indicated.• Emicizumab should not be injected into areas where the skin is red, bruised, tender, or hard or into areas where there are moles or scars.• In the clinic setting, patients will be monitored for signs of injection-site reactions in the period immediately following injections. Patients will be given guidance on reporting injection-site reactions when administering drug at home or after they leave the clinic.

Event	Action to Be Taken
Hypersensitivity Reaction, Anaphylaxis, Anaphylactoid Reaction	
 Suspected cases should be fully evaluated and treated as clinically indicated. Medicinal products for the treatment of hypersensitivity reactions (e.g., epinephrine, antihistamines, and glucocorticoids) and resuscitation equipment must be available for immediate use during the initial administrations in the infusion center, clinic, or hospital. If a patient has symptoms of anaphylaxis or severe hypersensitivity, administration of study drug must be immediately stopped and treatment of the reaction be initiated. No re-challenge should be performed in patients who experience a severe hypersensitivity, anaphylactic, or anaphylactoid reaction unless, after careful discussion with the medical monitor, the clinical benefit clearly outweighs the risk. The investigator should contact the Medical Monitor to assess if the clinical benefit clearly outweighs the risk to determine if and when the patient should resume taking emicizumab and discuss the patient's continued study participation. If the patient continues in the study, the next two scheduled doses must be in a monitored setting with at least a 60-minute observation period and resuscitation treatment immediately available. After each of these two doses in the clinic, the site will call the patient 24 hours after each dose to assess status of the patient. Investigators may order any pertinent laboratory tests, including an unscheduled anti-drug antibody, in the event any of these reactions occur.
Coagulation Disorder and Risk of Bleeding	
 HCPs should be vigilant for abnormal or unusual bleeding tendencies. Coagulation tests or other work-up may be indicated if judged to be appropriate by the investigator. If bleeding is observed, appropriate action as per local guidelines must be taken immediately.

5.1.4 Interpretation of Coagulation Assays for Patients Receiving Emicizumab

Emicizumab interacts with standard laboratory assays used in the management of patients with hemophilia A. In one-stage assays, emicizumab is associated with a supra-physiologically short time to clot formation and thus normalization of aPTT at subtherapeutic levels and an overestimation of true FVIII activity. Emicizumab is not recognized or neutralized by FVIII inhibitors and, therefore, cannot be detected by a functional test such as Bethesda or Nijmegen-Bethesda assays, which use a one-stage clotting-based readout. Emicizumab activity cannot be detected by chromogenic assays using purified bovine coagulation proteins and can only be detected using an assay composed of human proteins. [Table 5](#) summarizes the coagulation tests affected and unaffected by emicizumab. See the RO5543262 (Emicizumab) Investigator's Brochure for additional details on which tests can be used and how the test results can be interpreted.

Table 5 Coagulation Test Results Affected and Unaffected by Emicizumab

Results Affected by Emicizumab	Results Unaffected by Emicizumab

 • aPTT • Activated clotting time (ACT) • One-stage, aPTT-based, single-factor assays • aPTT-based Activated Protein C Resistance (APC-R) • Bethesda assays (clotting-based) for FVIII inhibitor titers 	
 • Thrombin time (TT) • One-stage, PT-based, single-factor assays • Chromogenic-based single-factor assays other than FVIIIa • Immuno-based assays (e.g., ELISA, turbidometric methods) • Bethesda assays (bovine chromogenic) for FVIII inhibitor titers • Genetic tests of coagulation factor mutations (e.g., Factor V Leiden, Prothrombin 20210)

FVIII = factor VIII.

^a For important considerations regarding FVIII chromogenic activity assays, please see information provided above in Section 5.1.4.

5.1.5 Procedure-Related Risks

Emicizumab is administered subcutaneously. Patients should be properly instructed to handle and prepare the injection and understand the risk for injection site reactions. See Section 5.1.2.1 for more information.

5.2 SAFETY PARAMETERS AND DEFINITIONS

Safety assessments will consist of monitoring and recording adverse events, including serious adverse events and adverse events of special interest, performing protocol-specified safety laboratory assessments, measuring protocol-specified vital signs, and conducting other protocol-specified tests that are deemed critical to the safety evaluation of the study.

Certain types of events require immediate reporting to the Sponsor, as outlined in Section 5.4.

5.2.1 Adverse Events

According to the ICH guideline for Good Clinical Practice, an adverse event is any untoward medical occurrence in a clinical investigation subject administered a pharmaceutical product, regardless of causal attribution. Therefore, an adverse event can be any of the following:

- Any unfavorable and unintended sign (including an abnormal laboratory finding), symptom, or disease temporally associated with the use of a medicinal product, whether or not considered related to the medicinal product

- Any new disease or exacerbation of an existing disease (a worsening in the character, frequency, or severity of a known condition), except as described in Section 5.3.5.10
- Recurrence of an intermittent medical condition (e.g., headache) not present at baseline
- Any deterioration in a laboratory value or other clinical test (e.g., ECG, X-ray) that is associated with symptoms or leads to a change in study treatment or concomitant treatment or discontinuation from study drug
- Adverse events that are related to a protocol-mandated intervention, including those that occur prior to assignment of study treatment (e.g., screening invasive procedures such as biopsies)

Bleeds considered as serious adverse events should be reported as serious adverse events on the eCRF. New nonserious bleeds, consistent with patients' pre-study disease, will not be considered adverse events and will not be recorded on the eCRF (but should be captured on the bleed/medication questionnaire).

5.2.2 Serious Adverse Events (Immediately Reportable to the Sponsor)

A serious adverse event is any adverse event that meets any of the following criteria:

- Is fatal (i.e., the adverse event actually causes or leads to death)
- Is life threatening (i.e., the adverse event, in the view of the investigator, places the patient at immediate risk of death)

This does not include any adverse event that had it occurred in a more severe form or was allowed to continue might have caused death.

- Requires or prolongs inpatient hospitalization (see Section 5.3.5.11)
- Results in persistent or significant disability/incapacity (i.e., the adverse event results in substantial disruption of the patient's ability to conduct normal life functions)
- Is a congenital anomaly/birth defect in a neonate/infant born to a mother exposed to study drug
- Is a significant medical event in the investigator's judgment (e.g., may jeopardize the patient or may require medical/surgical intervention to prevent one of the outcomes listed above)

The terms "severe" and "serious" are not synonymous. Severity refers to the intensity of an adverse event (e.g., rated as Grades 1–4, according to the WHO Toxicity Grading Scale for Determining The Severity of Adverse Events criteria; see Section 5.3.3); the event itself may be of relatively minor medical significance (such as severe headache without any further findings).

Severity and seriousness need to be independently assessed for each adverse event recorded on the eCRF.

Serious adverse events are required to be reported by the investigator to the Sponsor immediately (i.e., no more than 24 hours after learning of the event; see Section 5.4.2 for reporting instructions).

5.2.3 Adverse Events of Special Interest (Immediately Reportable to the Sponsor)

Adverse events of special interest are required to be reported by the investigator to the Sponsor immediately (i.e., no more than 24 hours after learning of the event; see Section 5.4.2 for reporting instructions). These may include suspected or confirmed cases. Adverse events of special interest for this study include the following:

- Cases of potential drug-induced liver injury that include an elevated ALT or AST in combination with either an elevated bilirubin or clinical jaundice, as defined by Hy's law (see Section 5.3.5.7)
- Suspected transmission of an infectious agent by the study drug, as defined below
 - Any organism, virus, or infectious particle (e.g., prion protein transmitting transmissible spongiform encephalopathy), pathogenic or non-pathogenic, is considered an infectious agent. A transmission of an infectious agent may be suspected from clinical symptoms or laboratory findings that indicate an infection in a patient exposed to a medicinal product. This term applies only when a contamination of the study drug is suspected.
- Systemic hypersensitivity reactions and anaphylactic and anaphylactoid reactions (see Sampson's Criteria in [Appendix 7](#))
- Thromboembolic events
- Microangiopathic hemolytic anemia or thrombotic microangiopathy (e.g., thrombotic thrombocytopenic purpura, hemolytic uremic syndrome)

5.3 METHODS AND TIMING FOR CAPTURING AND ASSESSING SAFETY PARAMETERS

The investigator is responsible for ensuring that all adverse events (see Section 5.2.1 for definition) are recorded on the Adverse Event eCRF and reported to the Sponsor in accordance with instructions provided in this section and in Sections 5.4–5.6.

For each adverse event recorded on the Adverse Event eCRF, the investigator will make an assessment of seriousness (see Section 5.2.2 for seriousness criteria), severity (see Section 5.3.3), and causality (see Section 5.3.4).

5.3.1 Adverse Event Reporting Period

Investigators will seek information on adverse events at each patient contact. All adverse events, whether reported by the patient or noted by study personnel, will be recorded in the patient's medical record and on the Adverse Event eCRF.

After informed consent has been obtained but prior to randomization (randomized arms) or initiation of study drug (non-randomized arm), only serious adverse events caused by a protocol-mandated intervention (e.g., invasive procedures such as biopsies, discontinuation of medications) should be reported (see Section 5.4.2 for instructions for reporting serious adverse events).

After randomization (randomized arms) or initiation of study drug (non-randomized arm), all adverse events will be reported until the patient completes his or her last study visit. After this period, the investigator should report any serious adverse events that are believed to be related to prior study drug treatment (see Section 5.6).

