Emicizumab will be administered as a SC injection in the home setting, with one dose every week or every 4 weeks, after a period of in-clinic administration and training. The first five drug administrations must be performed in a monitored setting, such as an infusion center, clinic, or hospital, with a 60-minute observation period following each of the first three doses. The observation period for the fourth and fifth doses will be at the investigator's discretion. For patients with a previous history of a clinically significant hypersensitivity reaction, additional precautions as described in Section 5.1.2.2 should be considered. At that time, the patient/caregiver will also have the opportunity to ask any questions of the HCP before the scheduled start of home administration. The

patient (≥ 7 years of age)/caregiver will observe at least one SC injection performed by the HCP and successfully administer at least one SC injection while being observed by a HCP prior to starting home administration. Each site will have the discretion to provide additional training if deemed appropriate. If, despite additional training, the investigator determines that the patient/caregiver is unable to inject emicizumab correctly, arrangements may be made to identify an alternative trained caregiver or HCP to administer the SC injections. At the investigator's discretion, study drug may be administered by a trained mobile nursing professional at the patient's home or another suitable location, if the patient has given written informed consent to participate in mobile nurse visits.

Patients/caregivers will be provided with the clinic contact information, to use in case they have questions related to self-administration between visits.

Medication administration errors during training will be documented in the electronic Case Report Form (eCRF). If necessary, patients or their HCP may choose to continue administration of study drug in the clinic. Compliance in the home setting is to be monitored by reviewing reported emicizumab use and recording collected used and unused vials at each site visit.

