6.5 SAFETY ANALYSES

The safety analyses population will be based on all enrolled patients grouped according to the actual treatment received. For Arm C patients, all safety data reported up to the day prior to switching will be included in the "control arm" safety summaries, and all safety data reported on or after the date of switching to active treatment will be reported separately.

Safety will be assessed for Arms A, B, and C and separately for Arm D through descriptive summaries of adverse events, laboratory test results (serum chemistry and hematology, including complete blood count with differential), ECGs, vital signs, and antibodies to emicizumab and FVIII.

To evaluate the overall safety of prophylactic emicizumab compared with no prophylaxis, the incidence of adverse events will be summarized and presented by System Organ Class mapped term, appropriate thesaurus level, and toxicity grade for each treatment arm.

For clinical laboratory data, summary statistics will be presented by treatment arm. In addition, shift tables describing changes from baseline will be presented using the WHO toxicity grading scale.

Data on the effect of immunogenicity (anti-emicizumab antibodies) on safety, efficacy, and/or clinical pharmacology and pharmacokinetics will be summarized adopting standard language/terminology (Shankar et al. 2014).

Although this is an open-label study, Sponsor personnel will not have access to safety summaries by treatment arm prior to the formal reporting of the study results. HCPs at participating study sites, as well as the Sponsor's drug safety and medical monitoring staff, will have access to the treatment assignments of patients for safety monitoring purposes only.

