Appendix 1-A Schedule of Assessments

Schedule of Assessments—Arms A and B																		
	Screen-ing ^a	Wk 1	Wk 2	Wk 3	Wk 4	Wk 5	Wk 7	Wk 9	Wk 13	Wk 17	Wk 21	Wk 25	Q8W from Wk 33	Wk 49	Q12W from Wk 61	Daily/weekly ^b	Study Comp/ET ^c	Early Disc. Safety F/U Visit before Study Comp ^d
Informed consent ^e	x																	
Inclusion/exclusion criteria	x																	
Medical history and demographics ^f	x																	
Physical examination (including weight) ^g	x	x				x					x		x			x	x	
Height	x										x		x					
Vital signs ^h	x	x ^h	x	x	x	x	x	x	x	x	x ^h	x	x ^h	x		x ^h	x	
Serum pregnancy test ⁱ	x	x																
Urine pregnancy test ⁱ		x			x		x	x	x	x	x	x	x	x		x	x	
Concomitant medications ^j	x	x			x		x	x	x	x	x	x	x	x		x	x	
ECG ^k	x	x ^k			x						x					x		
Safety laboratory assessments ⁱ	x ⁱ	x	x	x	x	x	x	x	x	x	x	x	x	x		x	x	
Bleed/medication questionnaire ^l															x			
Bleed/medication data review ^l		x			x		x	x	x	x	x	x	x	x		x	x	
Adverse events ^m		x	x	x	x	x	x	x	x	x	x	x	x	x		x	x	
IMP management ⁿ		x	x	x	x	x	x	x	x	x	x	x	x	x		x		
HRQoL and health status (EQ-5D-5L) ^o		x							x			x		x		x		
Emicizumab administration ^p		x	x	x	x	x	x	x	x	x	x	x	x	x	x	x		
PK/PD/ADA assessment ^q	See Appendix 2-A for details																	
Following treatment with bypassing agents ^r	Monitoring for thromboembolic events and thrombotic microangiography ^r																	

Emicizumab—F. Hoffmann-La Roche Ltd

114/Protocol YO39309, Version 5

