Appendix 1-A (cont.) Schedule of Assessments

Schedule of Assessments—Arm C (Screening to Switch to Emicizumab)								
	Screening ^a	Wk 1	Wk 5	Wk 9	Wk 13	Wk 17	Wk 21	Daily/weekly ^b
Informed consent ^e	x							
Inclusion/exclusion criteria	x							
Medical history and demographics ^f	x							
Physical examination (including weight) ^g	x	x						
Vital signs ^h	x	x ^h	x	x	x	x	x	
Height	x							
Serum pregnancy test ⁱ	x	x						
Urine pregnancy test ⁱ		x						
Concomitant medications ^j	x	x	x	x	x	x	x	
ECG ^k	x	x ^k						
Safety laboratory assessments ⁱ	x ⁱ	x						
Anti-FVIII antibodies	x							
Bleed medication questionnaire ^l								x
Bleed/injection data review ^s		x	x	x	x	x	x	
Adverse events ^m		x	x	x	x	x	x	
HRQoL and health status ^o		x			x			
PD biomarkers assessment ^q		x						

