Appendix 1-A (cont.) Schedule of Assessments

Disc =discontinuation; eCRF=electronic Case Report Form; ET=early termination; F/U=follow-up; FVIII=factor VIII; HRQoL=health-related Quality of Life; IMP=investigational medicinal product; Adapted Inhib-QoL =Inhibitor-Specific Quality of Life (with Aspects of Caregiver Burden); PD=pharmacodynamic; PK=pharmacokinetic; Q8W=every 8 weeks; Q12W=every 12 weeks; study comp.=study completion; Wk=week.

Notes: All assessments should be performed within \pm 2 days of the scheduled visit for the first 3 months, then \pm 7 days thereafter. PD and PK (trough) samples will be collected within \pm 2 days of the scheduled visit and linked to the timing from the dose. Clinic visits should coincide with the day of emicizumab dosing, and on those days the dose should be administered after blood draws and other assessments are conducted.

Unscheduled assessments may be performed at the discretion of the investigator and as clinically indicated. Except for the bleed/injection questionnaire, HRQoL, and health status, all other patient data will be collected during office or nurse visits. Evaluation at Week 25 or 49 will occur after a full 24 or 48 weeks in the study, respectively. Study completion evaluation occurs when a patient discontinues emicizumab or transitions into another study.

- ^a Screening may occur up to 4 weeks before Week 1 dosing.
- ^b Patients will complete the bleed/medication questionnaire at least weekly and at the time of a bleed, or when they take a hemophilia-related medication (including emicizumab). Arm B patients should indicate at least weekly whether or not they had a bleed.
- ^c There will be an Extension Phase in this study for all patients who have completed at least 52 weeks of treatment with prophylactic emicizumab and are still deriving clinical benefit. The study will be extending for 3 years after the last Arm D patient completes 1 year of treatment *and patients still having clinical benefit are transferred to a post-trial continued access solution per Roche Global Policy on Continued Access to Investigational Medicinal Products (Section 4.3.4). The study will end earlier, before 3 years after the last Arm D patient completes 1 year treatment, should the post-trial continued access solution be available earlier.*

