Appendix 1-A (cont.) Schedule of Assessments

- ⁱ Laboratory data (performed locally) include: complete blood count with differential (i.e., neutrophils, hemoglobin, platelet count), serum chemistries (i.e., sodium, potassium, glucose, blood urea nitrogen, creatinine, calcium, phosphorus, magnesium, total and direct bilirubin, albumin, alanine aminotransferase, aspartate aminotransferase, and alkaline phosphatase). Laboratory assessments completed at the screening visit do not have to be repeated at Week 1, if the period between screening and Week 1 is 5 days or less and there has been no change in health status as assessed by the investigator. Patients with childbearing potential will be required to have a negative serum pregnancy test result at screening (and within 7 days of study drug initiation, if applicable) and urine pregnancy tests performed at every clinic visit, with the exception of Weeks 2–4 and 7. Patients on Arm C will have urine pregnancy test performed at screening and before starting emicizumab (Week 25).
- ^j Concomitant medications (e.g., extra pain medication with bleed) will be asked about at the time of the monthly assessment, excluding treatments for bleeds (i.e., FVIII and other medications to treat bleeds), which will be collected on the bleeding questionnaire.
- ^k Performed locally. If screening ECG is abnormal, repeat at Week 1 (or Week 2 if screening and Week 1 occur on the same day), otherwise do not repeat. ECGs will also be performed 4–8 and 24 weeks after starting emicizumab or dose up-titration, as well as at study completion/early termination.
- ^l Reported by the patient or their caregivers and includes: start date and time, reason, type, location, and associated symptoms for joint and muscle bleeds, as well as start date and time, reason, type, and dose of each injection, excluding emicizumab.
- ^m Injection-site reaction adverse events will be collected on a separate form from the adverse event form. If there is unexpected worsening of the patient's hemophilia in terms of severity (e.g., increased number of doses of FVIII to stop bleeds compared with before study entry), frequency of bleeds, or nature at any time during the study, this should be documented as an adverse event on the Adverse Event eCRF, conveying that the underlying condition has changed by including applicable descriptors (e.g., "increased clinical severity of hemophilia").

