### **4.7.2 Adverse Events**

Adverse events will be summarized and presented by System Organ Class mapped term, appropriate thesaurus level, and toxicity grade (WHO Criteria) for each treatment arm. All adverse events will be coded using the current version of MedDRA at time of database closure. The total number and percentage of patients with at least one adverse event and total number of adverse events will be summarized. Separate adverse event summaries for serious adverse events, adverse events of special interest, severity, relatedness, and discontinuation/modification will be provided.

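### Adverse events are sought more often on emicizumab than in the control arm during the first 8 weeks, yet incidence is compared by arm with no matched window or caveat

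*Protocol*

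**What the plan says.** Protocol Section 5.3.1: "Investigators will seek information on adverse events at each patient contact". Section 5.3.2 asks for open, non-directive questions, and its first example looks back to the previous clinic visit.

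The Appendix 1-A grids mark adverse events at these visits up to Week 25:

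- Arms A and B: Weeks 1, 2, 3, 4, 5, 7, 9, 13, 17, 21 and 25.
- Arm C before the switch: Weeks 1, 5, 9, 13, 17 and 21, then Week 25, which is the switch visit.

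Footnote i treats the additional weeks as clinic visits: it requires "urine pregnancy tests performed at every clinic visit, with the exception of Weeks 2–4 and 7". They have a stated reason in Section 4.3.2: "The first five drug administrations must be performed in a monitored setting, such as an infusion center, clinic, or hospital".

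On analysis, Protocol Section 6.5 states: "To evaluate the overall safety of prophylactic emicizumab compared with no prophylaxis, the incidence of adverse events will be summarized", for each treatment arm. SAP Section 4.7.2 adds: "The total number and percentage of patients with at least one adverse event and total number of adverse events will be summarized". Neither section defines a window in which the visit schedules match, adjusts for contact frequency, or mentions that it differs.

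**The concern.** The safety objective for the randomized arms is a comparison with no prophylaxis. A by-arm table supports that comparison only if events are looked for with similar intensity in each arm. Here a patient starting emicizumab is questioned after 1 or 2 weeks, and a control patient after 4.

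The events most easily lost over a longer look-back are mild and brief. Table 6 of the protocol defines Grade 1 to include transient or mild discomfort of under 48 hours, and Section 1.2.2.3 reports that most events in the earlier Phase III studies were Grade 1 or 2. If some are forgotten, part of any early excess on emicizumab would reflect the schedule rather than the drug. This is separate from unequal follow-up: it would remain if all arms were cut to the same 24 weeks.

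**Working it through.** **Counting contacts.** Appendix 1-A fixes the week numbering: "Evaluation at Week 25 or 49 will occur after a full 24 or 48 weeks in the study, respectively". So the Week 9 visit falls after 8 full weeks. Because questioning looks back, the Week 9 visit is also the one that picks up events starting after the previous visit.

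- Contacts that can elicit onsets in the first 8 weeks: Weeks 2, 3, 4, 5, 7, 9 = 6 in Arms A and B; Weeks 5, 9 = 2 in Arm C.
- Post-baseline contacts through Week 25: 10 against 6.
- From Week 9 to Week 25 every arm is seen every 4 weeks.

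**Is there another route to the record?** Section 3.1 says events are recorded when they happen, but the only method of eliciting them that the protocol describes is questioning at contacts. The weekly handheld entry covers bleeds and hemophilia medication (Protocol Section 4.5.7, SAP Section 2.2.1). Section 5.3.5.13 says patient-reported data will not be reported as adverse events or reconciled with them.

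**Illustration of size.** The documents give no recall figure, so this rests on assumptions: equal true event rates in all arms, onsets spread evenly, and a chance of being recalled that decays exponentially until the next visit. For half-life h, k = ln 2 / h. An interval of L weeks contributes (1 − exp(−kL))/k captured weeks. Dividing the sum by the length of the period gives the share of events captured.

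Intervals in weeks are 1, 1, 1, 1, 2, 2 and then 4, 4, 4, 4 in Arms A and B, and six of 4 in Arm C.

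For h = 2, k = 0.3466, and the contributions are 0.845 (L = 1), 1.443 (L = 2) and 2.164 (L = 4).

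- First 8 weeks: A/B (4 × 0.845 + 2 × 1.443)/8 = 0.783; C (2 × 2.164)/8 = 0.541; ratio 1.45.
- 24 weeks: A/B (6.266 + 4 × 2.164)/24 = 0.622; C 0.541; ratio 1.15.

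| Assumed half-life (weeks) | Captured, first 8 weeks, A/B | Captured, first 8 weeks, C | Ratio, first 8 weeks | Ratio, 24 weeks |
|---|---|---|---|---|
| 1 | 63% | 34% | 1.87 | 1.29 |
| 2 | 78% | 54% | 1.45 | 1.15 |
| 4 | 88% | 72% | 1.22 | 1.07 |
| 8 | 94% | 85% | 1.11 | 1.04 |
| 16 | 97% | 92% | 1.05 | 1.02 |
| Perfect recall | 100% | 100% | 1.00 | 1.00 |

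The SAP also reports the percentage of patients with at least one event. If each patient has on average m such events in 24 weeks (Poisson), that percentage is 1 − exp(−m × share captured). With m = 1 it is 46.3% against 41.8% at h = 2, and 60.7% against 60.1% at h = 16. One of 14 planned controls is 1/14 = 7.1 percentage points, so on this measure the effect is smaller than one control patient.

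**What matches after Week 9.** The questioning does; the tests do not. The Arm C grid marks safety laboratory tests and ECGs only at screening and Week 1 until the Week 25 switch, while the Arms A and B grid marks safety laboratory tests throughout, and footnote k places an ECG 4 to 8 weeks after starting emicizumab. Section 3.1 says these assessments are the same for all patients apart from pharmacokinetics and anti-drug antibodies. That text and the Arm C grid need to be reconciled.

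**The case against.** **The excess is an inference.** It needs incomplete recall and visits as the main route to the record. Section 5.3.1 also covers events that patients report themselves. This stands: the direction follows if recall is incomplete, but the size cannot be taken from the documents.

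**Unscheduled contacts may offset the gap.** The sample-size section assumes annualized rates of 18 and 4, or about 18 × 8/52 = 2.8 and 4 × 8/52 = 0.6 bleeds per patient in 8 weeks. Section 4.5.5 requires laboratory tests within 24 to 48 hours of bypassing-agent use and does not limit this to emicizumab patients. This stands in part. The Arm C pre-switch grid has no row for that monitoring, and Appendix 9 does not expect bypassing agents in patients without inhibitors. If the cap of 55 non-inhibitor patients is filled, 70 − 55 = 15 have inhibitors, and 15 × 14/70 = 3 would be expected in Arm C. The net effect is uncertain.

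**The analysis is descriptive.** No test is applied, causality is judged event by event (Section 5.3.4), and the SAP plans separate summaries by relatedness, severity, seriousness and special interest. This stands. No type I error is at stake, and serious or special-interest events are less likely to be missed between visits.

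**The extra visits are justified, and any bias is cautious.** Early dosing is supervised by design, and over-detection on the drug errs towards finding harm. Both are true, but neither makes the arms comparable.

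A reader might infer a five-to-one imbalance by counting only visits before Week 9 (Weeks 2, 3, 4, 5 and 7 against Week 5). The documents do not support that as the measure for early onsets, because the Week 9 questioning reaches back over Weeks 5 to 8 in every arm.

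**Conclusion.** The imbalance in scheduled questioning is a fact of the schedule: six contacts against two for onsets in the first 8 weeks, none afterwards. Both documents compare incidence by arm without acknowledging it. The likely consequence is a modest over-recording of mild, transient, non-serious events on emicizumab. Within a common 24-week window the illustration gives about 2% to 15% more recorded events for half-lives of 16 down to 2 weeks, more if recall fades faster, and none if recall is perfect. These figures assume equal true rates, exponential loss of recall and no unscheduled contacts.

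Two stronger readings are not supported. A reader might infer that early events are in fact found more often on emicizumab and will be counted as drug effects. That depends on recall, which the documents do not quantify, and relatedness is assessed separately. A reader might also infer that early differences should be presumed not to be drug effects. Nothing in the documents justifies that, and it would discount genuine reactions confined to the loading period. This is a cheap improvement to reporting; it does not undermine the safety evaluation.

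**What to change.** In SAP Section 4.7.2:

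1. Add a supplementary by-arm table of adverse events with onset from the Week 9 visit to the day before Week 25. Exclude events detected only through scheduled laboratory tests or ECGs, which Arm C does not have in that window.
2. Add one sentence stating that elicitation was more frequent on emicizumab before Week 9, and that between-arm differences in early non-serious events should be interpreted with that in mind.
3. Keep the full-period table as the main display, and adopt no rule that presumes early differences are unrelated to the drug.

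The cost is one output and one sentence. The table needs onset dates, visit dates and a check of how each event was detected, with no new visits. Its drawbacks should be stated beside it: it leaves out the loading period, and it is imprecise, with about 14 controls over 16 weeks (14 × 16/52 = 4.3 patient-years).
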